**Table 4: Schedule of Events for Follow-up Period of Patients Who Undergo Joint Replacement Surgery**

Follow-up Study Day (Visit window, days)	Post-Operative 	Long-Term 
	Follow-up Visit 1 4 weeks after joint replacement surgery	Follow-up Visit 2 20 weeks after joint replacement surgery
	Follow-up Day 29 (±7)	Follow-up Day 140 (±7)
Collection of surgically resected tissue for histological and molecular analyses		X
Treatment		
Concomitant medications and therapy	X	X
Safety		
Medical history related to the joint replacement	X	X
Adverse events	→	
Vital signs	X	X
Physical examination with joint exam	X	X
Knee Society Score 	X	X
Radiograph of knees, hips, and shoulders (bilateral)		X

1. Any patient who has joint replacement surgery during the study up to the end of the Follow-Up period at week 36 is to be asked to return to the site at 4 and 20 weeks after the surgery date for safety evaluations. Relevant information related to the surgery is collected at the week-4 visit, including placement of the prosthesis and healing of the surgical wound. The visit at 20 weeks after surgery includes an assessment of OA progression (including repeat radiographs of both knees) and the collection of any information about joint-related pain or AEs (including joint replacement) that may have taken place since the last clinic visit.
2. Formal post-operative assessment of joint replacements is to be done by completing the Knee Society Score questionnaire for knee replacements.

## 11.2. Reference for Criteria for Treatment-Emergent Potentially Clinically Significant Values (PCSV)

The PCSV criteria below should be used as a reference; the actual criteria for each study should be determined and agreed to by the study team prior to database lock as part of SAP and should be based on the study population, indication, and potential effects of study treatment.

**Table 5: Criteria for Treatment-Emergent Potentially Clinically Significant Values (PCSV)**

Parameter	Treatment-Emergent PCSV	Comments
Clinical Chemistry		
ALT*	
 
>3 and <math>\leq</math> 5 ULN and baseline <math>\leq</math> 3 ULN*
 
>5 and <math>\leq</math> 10 ULN and baseline <math>\leq</math> 5 ULN
 
>10 and <math>\leq</math> 20 ULN and baseline <math>\leq</math> 10 ULN
 
>20 ULN and baseline <math>\leq</math> 20 ULN
 
	
 
Enzyme activity must be expressed in ULN, not in IU/L.
 
FDA DILI Guidance July 2009.
 
Each category is calculated independently.
 
* At least one level is required; multiple levels are optional for phase 2/3 studies. If it is desirable to get the distribution across the different PCSV levels, additional shift table on <math>\leq</math>3, >3 to <math>\leq</math>5, >5 to <math>\leq</math>10, >10 to <math>\leq</math>20, and >20 category for baseline vs. post baseline may be provided
 

AST*	
 
>3 and <math>\leq</math> 5 ULN and baseline <math>\leq</math> 3 ULN*
 
>5 and <math>\leq</math> 10 ULN and baseline <math>\leq</math> 5 ULN
 
>10 and <math>\leq</math> 20 ULN and baseline <math>\leq</math> 10 ULN
 
>20 ULN and baseline <math>\leq</math> 20 ULN
 
	
 
Enzyme activity must be expressed in ULN, not in IU/L.
 
FDA DILI Guidance July 2009.
 
Each category is calculated independently.
 
* At least one level is required; multiple levels are optional for phase 2/3 studies. If it is desirable to get the distribution across the different PCSV levels, additional shift table on <math>\leq</math>3, >3 to <math>\leq</math>5, >5 to <math>\leq</math>10, >10 to <math>\leq</math>20, and >20 category for baseline vs. post baseline may be provided
 

Alkaline Phosphatase	>1.5 ULN and baseline $\leq$ 1.5 ULN	
 
Enzyme activity must be expressed in ULN, not in IU/L.
 
FDA DILI Guidance July 2009.
 

Parameter	Treatment-Emergent PCSV	Comments
Total Bilirubin*	>1.5 and $\leq$ 2 ULN and baseline $\leq$ 1.5 ULN*  >2 ULN and baseline $\leq$ 2.0 ULN	Must be expressed in ULN, not in $\mu\text{mol/L}$ or mg/L. Categories are cumulative.  FDA DILI Guidance July 2009.  * At least one level is required; multiple levels are optional for phase 2/3 studies. If it is desirable to get the distribution of significant level, additional shift table on $\leq$ 1.5, >1.5 to $\leq$ 2.0 and > 2.0 category for baseline vs. post baseline may be provided
CPK*	>3 and $\leq$ 10 ULN and baseline $\leq$ 3ULN*  >10 ULN and baseline $\leq$ 10ULN	FDA Feb 2005.  Am J Cardiol April 2006.  Categories are cumulative.  * At least one level is required; multiple levels are optional for phase 2/3 studies. If it is desirable to get the distribution of significant level, additional shift table on $\leq$ 3, >3 to $\leq$ 10, and > 10 category for baseline vs. post baseline may be provided
Creatinine	$\geq$ 150 $\mu\text{mol/L}$ (Adults) and baseline $<$ 150 $\mu\text{mol/L}$ $\geq$ =30% change from baseline and $<$ 100% change from baseline $\geq$ 100% change from baseline	Benichou C., 1994  3 independent criteria
Uric Acid		Harrison - Principles of internal Medicine 17 th Ed., 2008.
Hyperuricemia	>408 $\mu\text{mol/L}$ and $\leq$ =408 $\mu\text{mol/L}$ at baseline	Two independent criteria
Hypouricemia	$<$ 120 $\mu\text{mol/L}$ and $\geq$ 120 $\mu\text{mol/L}$ at baseline	
Blood Urea Nitrogen	$\geq$ 17 mmol/L and $<$ 17 mmol/L at baseline	Two independent criteria

Parameter	Treatment-Emergent PCSV	Comments
Chloride		Two independent criteria
Hypochloremia	<80 mmol/L and baseline $\geq$ 80 mmol/L	
Hyperchloremia	>115 mmol/L and baseline $\leq$ 115 mmol/L	
Sodium		Two independent criteria
Hyponatremia	$\leq$ 129 mmol/L and baseline $>$ 129 mmol/L	
Hypernatremia	$\geq$ 160 mmol/L and baseline $<$ 160 mmol/L	
Potassium		FDA Feb 2005.
Hypokalemia	<3 mmol/L and baseline $\geq$ 3 mmol/L	Two independent criteria
Hyperkalemia	$\geq$ 5.5 mmol/L and baseline $<$ 5.5 mmol/L	
Glucose		
Hypoglycaemia	( $\leq$ 3.9 mmol/L and $<$ LLN) and ( $>$ 3.9 mmol/L or $\geq$ LLN) at baseline	ADA May 2005.
Hyperglycaemia	$\geq$ 11.1 mmol/L (unfasted); $\geq$ 7 mmol/L (fasted) and $<$ 11.1 mmol/L (unfasted); $<$ 7 mmol/L (fasted) at baseline	ADA Jan 2008.
Albumin	$\leq$ 25 g/L and $>$ 25 g/L at baseline	
hs-CRP	2 ULN or $>$ 10 mg/L (if ULN not provided)	FDA Sept. 2005

Parameter	Treatment-Emergent PCSV	Comments
Hematology		
WBC	<3.0 Giga/L and >=3.0 Giga/L at baseline (Non-Black); <2.0 Giga/L and >=2.0 Giga/L at baseline (Black) ≥16.0 Giga/L and < 16 Giga/L at baseline	Increase in WBC: not relevant.  To be interpreted only if no differential count available.
Lymphocytes	>4.0 Giga/L and <= 4.0 Giga/L at baseline	
Neutrophils	<1.5 Giga/L and >=1.5 Giga/L at baseline (Non-Black); <1.0 Giga/L and >=1.0 Giga/L at baseline (Black)	International Consensus meeting on drug-induced blood cytopenias, 1991. FDA criteria.
Monocytes	>0.7 Giga/L <= 0.7 Giga/L at baseline	
Basophils	>0.1 Giga/L <= 0.1 Giga/L at baseline	
Eosinophils	(>0.5 Giga/L and >ULN) and (<=0.5 Giga/L or <= ULN at baseline)	Harrison - Principles of internal Medicine 17 th Ed., 2008.
Hemoglobin	≤115 g/L and > 115 g/L at baseline for male; ≤95 g/L and > 95 g/L at baseline for Female. ≥185 g/L and <185 g/L at baseline for Male; ≥165 g/L and < 165 g/L at baseline for Female  Decrease from Baseline ≥20 g/L	Three criteria are independent.  Criteria based upon decrease from baseline are more relevant than based on absolute value. Other categories for decrease from baseline can be used (≥30 g/L, ≥40 g/L, ≥50 g/L).
Hematocrit	≤0.37 v/v and > 0.37 v/v at baseline for Male ; ≤0.32 v/v and > 0.32 v/v at baseline for Female  ≥0.55 v/v and < 0.55 v/v at baseline for Male ; ≥0.5 v/v and < 0.5 v/v at baseline for Female	Two Criteria are independent

Parameter	Treatment-Emergent PCSV	Comments
RBC	Female $<3$ Tera/L and baseline $\geq 3$ Tera/L $\geq 6$ Tera/L and baseline $< 6$ Tera/L Male $<4$ Tera/L and baseline $\geq 4$ Tera/L $\geq 7$ Tera/L and baseline $< 7$ Tera/L	Unless specifically required for particular drug development, the analysis is redundant with that of Hb. Otherwise, consider FDA criteria.
Platelets	$<100$ Giga/L and $\geq 100$ Giga/L at baseline $\geq 700$ Giga/L and $< 700$ Giga/L at baseline	International Consensus meeting on drug-induced blood cytopenias, 1991. Two independent criteria
Urinalysis		
pH	$\leq 4.6$ and $> 4.6$ at baseline $\geq 8$ and $< 8$ at baseline	Two independent criteria
Vital signs		
HR	$\leq 50$ bpm and decrease from baseline $\geq 20$ bpm $\geq 120$ bpm and increase from baseline $\geq 20$ bpm	To be applied for all positions (including missing) except STANDING.
SBP	$\leq 95$ mmHg and decrease from baseline $\geq 20$ mmHg $\geq 160$ mmHg and increase from baseline $\geq 20$ mmHg	To be applied for all positions (including missing) except STANDING.
DBP	$\leq 45$ mmHg and decrease from baseline $\geq 10$ mmHg $\geq 110$ mmHg and increase from baseline $\geq 10$ mmHg	To be applied for all positions (including missing) except STANDING.

Parameter	Treatment-Emergent PCSV	Comments
Orthostatic Hypotension	
Su SBP < 160 mmHg -
 
SBP St – Su <math>\leq</math> - 20 mmHg
 
DBP St – Su <math>\leq</math> - 10 mmHg
 
Su SBP <math>\geq</math> 160 mmHg -
 
SBP St – Su <math>\leq</math> - 30 mmHg
 
DBP St – Su <math>\leq</math> - 15 mmHg
 
and
 
HR change: <math>\geq</math>30 bpm from semi-recumbent to standing
	
Weight	
<math>\geq</math>5% increase from baseline
 
<math>\geq</math>5% decrease from baseline
	FDA Feb 2007.
ECG		Ref.: CPMP 1997 guideline. ICH E14 2005
HR(ECG)	$\leq$ 50 bpm and decrease from baseline $\geq$ 20	
Ventricular Rate bpm (beats/min) in the data	
bpmin <math>\geq</math>120 bpm and increase from baseline
 
<math>\geq</math>20 bpm
	
PR/PQ	$\geq$ 220 ms and increase from baseline $\geq$ 20 ms	
QRS	$\geq$ 120 ms & < 120 ms at baseline	
QTcF	
Absolute values (ms)
 
<math>></math>450 ms and baseline <math>\leq</math>450 ms
 
<math>></math>480 ms and baseline <math>\leq</math>480 ms
 
<math>></math>500 ms and <math>\leq</math> 500 ms at baseline
 
Increase from baseline
 
Increase from baseline 30-60 ms
 
Increase from baseline <math>></math>60 ms
	
To be applied to any kind of QT correction formula.
 
<math>\Delta</math>QTc<math>></math>60 ms are the PCSA to be identified in individual subjects/patients listings.

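### SAP Table 5 caps the starred ALT/AST, bilirubin and CPK levels, so no required summary guarantees the number of patients above 3 times ULN, and the bilirubin and CPK rows contradict themselves

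*SAP*

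**What the plan says.** SAP Table 5 gives four treatment-emergent levels each for ALT and AST, in multiples of ULN: above 3 up to 5 (baseline at most 3), above 5 up to 10 (baseline at most 5), above 10 up to 20 (baseline at most 10), and above 20 (baseline at most 20). The lowest level carries an asterisk, and so does the analyte name. The comment column says "Each category is calculated independently". The asterisk note says "At least one level is required; multiple levels are optional for phase 2/3 studies". It then offers a shift table over the full set of bands, but only as an option: "category for baseline vs. post baseline may be provided".

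Total bilirubin has a starred level above 1.5 up to 2 (baseline at most 1.5) and a second level above 2. CPK has a starred level above 3 up to 10 (baseline at most 3) and a second level above 10. Both rows repeat the one-level note, but their counting rule is the opposite: "Categories are cumulative".

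SAP 5.8.2 commits to a PCSV summary by treatment group, a PCSV listing, and laboratory listings that flag out-of-range values. The SAP Version 2.0 change table (SAP 1.2.4.2) removes the general laboratory shift tables because the PCSV analysis is considered enough. It also removes the combined ALT/AST-and-bilirubin criteria.

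**The concern.** Readers of a liver safety table want to know how many patients went above 3 times ULN. A level with an upper bound does not answer that. If only the starred level is tabulated, as the note permits, the patients with the largest rises are the ones who can be missing from it. If every level is tabulated, the separate counts still cannot be added.

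Skipping a band is plausible with this schedule. Protocol Table 1 has post-baseline chemistry at weeks 4, 8, 12, 16, 24 and 36, so consecutive scheduled samples are 4 to 12 weeks apart and a rise can pass through 3 to 5 times ULN unrecorded.

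The PCSV table also carries more weight than usual, because Version 2.0 relies on it in place of the shift tables. The protocol permits acetaminophen rescue with an explicit liver caution (7.2).

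For bilirubin and CPK, two programmers could follow the same row and produce different first-level counts.

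**Working it through.** The plan states no figure to reproduce; this is a check of counting rules. The rules are taken literally from Table 5: a patient counts at a level if any post-baseline value lies in the band and the baseline condition is met. The seven ALT patients below are invented to exercise the rules. They are not trial data. Values are multiples of ULN.

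| Patient | Baseline | Post-baseline values | Levels met, bands as written | Levels met, lower bounds only |
|---|---|---|---|---|
| A | 1 | 1, 4 | >3–5 | >3 |
| B | 1 | 1, 6, 1 | >5–10 | >3, >5 |
| C | 1 | 12 | >10–20 | >3, >5, >10 |
| D | 1 | 4, 8, 2 | >3–5 and >5–10 | >3, >5 |
| E | 1 | 25 | >20 | >3, >5, >10, >20 |
| F | 4 | 7 | >5–10 | >5 |
| G | 4 | 4.5 | none | none |

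**Target number.** Patients with baseline at most 3 and any value above 3: A, B, C, D, E = 5.

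**Starred level only.** A and D = 2. B, C and E are not counted, so 5 − 2 = 3 are missing.

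**All four levels.** Counts are 2, 3, 1, 1.
- Sum: 2 + 3 + 1 + 1 = 7. Patient D is counted twice, and F enters at >5–10 from a baseline of 4.
- Distinct patients in any level: A to F = 6.
- Neither 7 nor 6 equals 5.

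The definition in SAP 5.8.2 is narrower and requires a normal value at screening and baseline. If it governs, F drops out: the levels become 2, 2, 1, 1, which sum to 6, with 5 distinct patients. The double count of D remains, so the rows still do not add up to 5.

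**Is anyone lost if all four levels are run?** No. A grid of baselines 0 to 3 and single post-baseline values 3.1 to 39.9 found 0 combinations outside all four levels. On the same 0.1-step grid, the smallest single value missed by the starred level is 5.1.

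**Lower bounds only.** Counts are 5, 5, 2, 1. The first row equals the target number of 5 directly.

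**Bilirubin and CPK.** The row text and its comment give different answers for the same patient:

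| Case | Band text: first level, second level | Cumulative comment: first level, second level |
|---|---|---|
| Bilirubin 1 → 2.5 | no, yes | yes, yes |
| CPK 1 → 12 | no, yes | yes, yes |

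The first-level count therefore depends on which statement is programmed.

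**The case against.** A reader might infer that the number above 3 times ULN can never be produced. The documents do not support that. The four ALT/AST levels together cover every value above 3, and the top one is open-ended. The optional shift table would give the number if it used each patient's worst post-baseline value. Listings are also planned, although a PCSV listing limited to the starred definition would omit the same patients; the out-of-range flags would still show them.

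A reader might also infer that bilirubin above 2 or CPK above 10 times ULN is definitely dropped from the first level. That holds only if the band text overrides the cumulative comment.

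That the starred band is the one required level is an inference. The note does not name a level, and the asterisk on the analyte name may simply mark the footnote. Version 2.0 pruned this appendix and kept all four ALT/AST levels, which fits an intention to report them. This stands as a limit: the omission is permitted by the text, not prescribed by it.

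Appendix 11.2 calls Table 5 a reference. That does not cure the problem. The same sentence says the actual criteria are to be settled as part of the SAP before database lock, SAP 5.8 and 5.8.2 point to this appendix for the definitions, and Version 2.0 edited it for this study.

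A link to Hy's law is tempting. Protocol 7.3.2.1 uses a 3-fold ALT/AST and 2-fold bilirubin criterion, but as a dosing rule for the individual patient, and it needs both elevations together. Single-analyte counts would not give that number even with the levels corrected.

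Finally, Version 2.0 reports no new safety findings at week 12 and plans an abbreviated report. No efficacy or multiplicity result is touched. This limits the consequence but does not make the table unambiguous.

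**Conclusion.** The point holds in this form. For ALT and AST, a patient who jumps over the band is not counted at the starred level, the levels cannot be summed, and no required summary guarantees the number above 3 times ULN. It can be recovered only from the patient-level results of all four levels, from the optional shift table, or from listings. For bilirubin and CPK the certain defect is that the cumulative comment conflicts with the upper bounds.

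The size can be shown only by example: 2 counted at the starred level against 5 truly above 3 times ULN, and a sum of 7 when all levels are run. This rests on the literal any-value-in-band reading and on invented patients. The documents give no basis for how often a band would be skipped in this trial, and nothing in them shows that a patient was missed.

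**What to change.** Define each level by its lower bound only: ALT/AST above 3, 5, 10 and 20 times ULN; bilirubin above 1.5 and 2; CPK above 3 and 10. Keep the condition that baseline is at or below the same threshold. State that levels are cumulative on the worst post-baseline value, and delete the ALT/AST comment about independent calculation. Table 5 already uses this form for alkaline phosphatase and for the absolute QTcF values. Add a footnote that the rows are not strictly nested, because the baseline condition loosens with the level: patient F above counts at >5 but not at >3.

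An equally valid alternative keeps the bands, assigns each patient to one band by worst post-baseline value, and adds a required total row for any value above the lowest threshold. That row must be computed directly. By worst value the seven patients give 1, 3, 1, 1, which sums to 6, while the total row (baseline at most 3) is 5.

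Either way, say which levels will be reported. The cost is one table edit and one program change, with no new data. If PCSV tables were already produced for the week-12 analysis, rerun them on the same definition. This does not by itself supply a combined ALT/AST-plus-bilirubin count.

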### 8.2.3.2. Orthostatic Vital Sign Assessment

Orthostatic blood pressure and heart rate are measured with the patient lying semi-recumbent for 10 minutes and after standing for 2 minutes. Prior to starting an assessment of orthostatic blood pressure and heart rate, patients should ambulate for at least 5 minutes. This assessment will be performed at the specified visits ([Table 1](#)).

In case any of the following criteria are met, up to 2 re-checks (within approximately 5 minutes of the original measurement) should be performed (patient should remain standing):

If the semi-recumbent systolic blood pressure is <160 mm Hg, a decrease in the 2-minute standing systolic blood pressure of  $\geq 20$  mm Hg or a decrease in the standing diastolic blood pressure of  $\geq 10$  mm Hg from the semi-recumbent systolic or diastolic blood pressure, respectively

OR

If the semi-recumbent systolic blood pressure is  $\geq 160$  mm Hg, a decrease in the 2-minute standing systolic blood pressure of  $\geq 30$  mm Hg or a decrease in the standing diastolic blood pressure of  $\geq 15$  mm Hg from the semi-recumbent systolic or diastolic blood pressure, respectively

OR

An increase in the 2-minute standing heart rate of  $\geq 30$  bpm from the semi-recumbent heart rate.

An AE of orthostatic vital sign change should be reported if the change is confirmed upon the repeat tests.

If the patient is unable to stand for standing blood pressure measurements due to dizziness or lightheadedness, the patient is considered to have orthostatic hypotension, which should be reported.

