#### 10.4.4. Safety Analysis

The safety data including TEAEs and other safety information (clinical laboratory evaluations, vital signs and 12-lead ECG) will be summarized by treatment groups.

Thresholds for potentially clinically significant values (PCSVs) in laboratory parameters and vital signs will be defined by the sponsor and be in effect at the time of the final SAP approval.

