#### **4.5.7. Vital Signs**

The following vital signs parameters are to be collected according to the Schedule of Events in [Table 3](#):

- Body temperature (°C)
- Semi-recumbent/2-minute standing systolic and diastolic blood pressures (mmHg) and heart rate (bpm)
- Respiratory rate (bpm)

Both actual values and “change from baseline” values (defined as the post-baseline value minus the baseline value) are to be used in the result summaries. Potentially clinically significant values (PCSV) ranges are to be applied to the vital sign parameter values as applicable (see Appendix 11.2 for PCSV definitions).

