#### 4.5.8. Orthostatic Hypotension

A patient is to be determined to have orthostatic hypotension if any of the following criteria are met:

- If the semi-recumbent systolic blood pressure is  $<160$  mm Hg, a decrease in the 2-minute standing systolic blood pressure of  $\geq20$  mm Hg or a decrease in the standing diastolic blood pressure of  $\geq10$  mm Hg from the semi-recumbent systolic or diastolic blood pressure, respectively

OR

- If the semi-recumbent systolic blood pressure is  $\geq160$  mm Hg, a decrease in the 2-minute standing systolic blood pressure of  $\geq30$  mm Hg or a decrease in the standing diastolic blood pressure of  $\geq15$  mm Hg from the semi-recumbent systolic or diastolic blood pressure, respectively

OR

- An increase in the 2-minute standing heart rate of  $\geq30$  bpm from the semi-recumbent heart rate.

OR

- The patient is unable to stand for standing blood pressure measurements due to dizziness or lightheadedness

In case any of the following criteria are met, up to 2 re-checks (within approximately 5 minutes of the original measurement) should be performed (patient should remain standing). An AE of orthostatic vital sign change should be reported if the change is confirmed upon the repeat tests.

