## 5.8. Analysis of Safety Data

The analysis of safety and tolerability is to be performed on the SAF, as defined in Section 3.2.

The safety analysis is to be based on the reported AEs and other safety information (clinical laboratory evaluations, vital signs, 12-lead ECG, Physical Examination, etc.) and is to be summarized by treatment group.

Treatment-Emergent Potential Clinically Significant Values (PCSV) in laboratory variables, vital signs and ECG are defined in Appendix 11.2.

The summary of safety results will be presented for each treatment group and by visit where applicable.

**Study observation period:** The observation period is divided into the four segments defined in Section 5.

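### SAP Table 5 and SAP 4.5.8 define orthostatic hypotension differently, and the SAP gives conflicting directions on which one drives the PCSV summary

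*SAP*

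**What the plan says.** SAP 4.5.8 opens with "A patient is to be determined to have orthostatic hypotension if any of the following criteria are met" and joins four items by OR:

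- a systolic fall of at least 20 or a diastolic fall of at least 10 mm Hg when semi-recumbent systolic pressure is below 160;
- a systolic fall of at least 30 or a diastolic fall of at least 15 mm Hg when it is 160 or above;
- a standing heart-rate increase of at least 30 bpm;
- "The patient is unable to stand for standing blood pressure measurements due to dizziness or lightheadedness".

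Protocol 8.2.3.2 joins the same blood-pressure and heart-rate items by OR, as triggers for re-checks and for reporting an adverse event. Of a patient who cannot stand because of dizziness or lightheadedness it says that "the patient is considered to have orthostatic hypotension, which should be reported".

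SAP 11.2, Table 5, row Orthostatic Hypotension, lists the systolic and diastolic falls for the two strata with the same thresholds, then the word *and*, then a heart-rate change of at least "30 bpm from semi-recumbent to standing". It has no inability-to-stand line, and its comment cell is empty.

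On which definition applies, the SAP points two ways. Section 5.8 says that PCSVs "in laboratory variables, vital signs and ECG are defined in Appendix 11.2", section 4.5.7 sends vital-sign PCSVs to the same appendix, and section 5.8.3 plans a PCSV summary and listing that include orthostatic hypotension. Footnote 5 to the schedule of events, in both documents, instead refers the reader to protocol 8.2.3.2 for defining orthostatic hypotension.

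**The concern.** Two programmers working from the same SAP could produce different orthostatic hypotension counts for the summary in section 5.8.3, and each could cite a section in support. One would follow 4.5.8 and count anyone meeting a single criterion. The other would follow Table 5 and could require a heart-rate change in addition to a blood-pressure fall. A patient too dizzy to stand, with no standing values, could not enter the Table 5 count at all.

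No other PCSV row fills the gap. The heart-rate, systolic and diastolic rows of Table 5 each carry the comment "To be applied for all positions (including missing) except STANDING", so the orthostatic row is the only PCSV row that uses standing values. Protocol 3.2.1 lists effects on blood pressure among the potential risks behind the planned monitoring, so the flag should have one meaning.

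**Working it through.** There is no planned figure to reproduce. The check compares the two definitions over every combination of criteria that one assessment can show.

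**Inputs.** SAP 4.5.8 supplies the OR logic, the thresholds and the inability-to-stand item. Table 5 supplies the same thresholds, the printed *and*, and no inability-to-stand item. SAP 6.3 says missing vital signs are not imputed, so absent standing values stay absent.

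**States.** Let S be systolic fall met, D diastolic fall met, H heart-rate rise of at least 30 bpm, and U unable to stand with no standing values. Each semi-recumbent systolic stratum (below 160, or 160 and above) has 2 × 2 × 2 = 8 combinations of S, D and H, plus one U state. That gives 2 × 9 = 18 states.

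**SAP 4.5.8.** S or D or H or U is positive in all but the one empty state of each stratum: 18 − 2 = 16.

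**Table 5.** The row does not print how its systolic and diastolic lines combine, or how far *and* reaches, so four readings were tried. H was taken as a rise.

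| Reading of the row | Positive states | 4.5.8 states missed |
|---|---|---|
| A. (S or D) and H | 2 × 3 = 6 | 10 |
| B. (S and D) and H | 2 × 1 = 2 | 14 |
| C. *and* applies only to the 160-and-above block | 6 + 3 = 9 | 7 |
| D. *and* is only a list separator, so S or D or H | 2 × 7 = 14 | 2 |

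No reading matches 4.5.8. The two states missed under D are the two U states.

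**Examples under reading A.**

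- Semi-recumbent systolic 130, systolic fall 25, diastolic fall 5, heart-rate rise 10: positive under 4.5.8, negative under Table 5.
- Semi-recumbent systolic 130, no pressure fall, heart-rate rise 32: positive under 4.5.8, negative under Table 5.
- Semi-recumbent systolic 130, systolic fall 25, diastolic fall 12, heart-rate rise 32: positive under both.

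**Direction.** Under A, B and C every flagged patient has a blood-pressure fall, and that alone satisfies 4.5.8. These readings therefore flag the same patients as 4.5.8 or fewer, whatever heart-rate *change* means. Under D the heart-rate line stands alone. If *change* were read as an absolute change, a patient whose heart rate fell by 30 bpm would be flagged by Table 5 but not by 4.5.8, which says *increase*.

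**Size.** The states are logical patterns, not patients. Under reading A, let c be the share of blood-pressure-fall cases that also have the heart-rate rise, and r the ratio of heart-rate-only plus unable-to-stand cases to blood-pressure-fall cases. The share missed is 1 − c/(1 + r). The documents give neither quantity. Assumed values show the range:

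- c = 1, r = 0: 0%
- c = 0.5, r = 0: 1 − 0.5/1 = 50%
- c = 0.5, r = 1: 1 − 0.5/2 = 75%
- c = 0: 100% for any r

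**The case against.** The strongest reply is that the documents already settle the definition. Two full-text sections, SAP 4.5.8 and protocol 8.2.3.2, agree on the OR structure and on inability to stand, and footnote 5 names the protocol section as the place of definition. On this view Table 5 is a shorthand row in an appendix whose introduction calls its criteria a reference. This has weight: it makes a drafting slip more likely than two rival definitions. It does not remove the conflict, because SAP 4.5.7 and 5.8 expressly send PCSVs to the appendix. Its introduction says that the actual criteria are to be agreed as part of the SAP, and the SAP contains no other set. Version 2.0 deleted other rows from this table and kept this one.

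Protocol 10.4.4 says PCSV thresholds "will be defined by the sponsor and be in effect at the time of the final SAP approval". That does not make Table 5 override 4.5.8, because the numerical thresholds are the same in both. The connectors, the wording of the heart-rate item and the non-numeric item differ.

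It can also be said that inability to stand is not a measured value and may not belong in a table of value ranges. That is fair, but the SAP should then say so, because 4.5.8 counts it.

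A reader might infer more in three ways, none supported:

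- **That Table 5 can only undercount.** This holds where the row requires a blood-pressure fall, but not for the list reading combined with an absolute heart-rate change.
- **That a known fraction of cases is lost.** The state counts depend on connectors that the row does not print, and they are not frequencies.
- **That a safety signal would be hidden.** Confirmed orthostatic changes are still reported as adverse events, and orthostatic values are still summarised. Protocol 3.2.1 also says there is at present no evidence linking the anti-NGF safety concerns to blocking this receptor.

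**Conclusion.** The inconsistency stands, with minor severity. SAP 4.5.8 and Table 5 do not define the same set of patients, and the SAP does not say which definition drives the orthostatic hypotension output. With *and* read as a conjunction between the blood-pressure falls and the heart-rate change, Table 5 flags the same patients as 4.5.8 or fewer. Read as a loose list, it still misses those who qualify only by inability to stand.

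The textual mismatch is certain. The size of the difference in counts is unknown and cannot be derived from the documents. The consequence is confined to one descriptive PCSV summary and its listing, and no hypothesis test or endpoint uses the flag. The comparison assumes that a patient recorded as unable to stand has no standing values at that assessment.

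**What to change.** Reconcile SAP Table 5, SAP 4.5.8 and protocol 8.2.3.2 into one definition. Write out every AND and OR, including those between the systolic and diastolic lines and between the two strata, and state the direction of the heart-rate change. Say whether inability to stand enters the PCSV flag and, if so, from which record it is taken. Name in SAP 5.8.3 the definition that drives the summary and listing, and make footnote 5 agree with it. Which clinical rule applies is for the study team; this point asks only that there be one.

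The cost is one table row, one derivation and a cross-reference sentence. Standing measurements are already scheduled and inability to stand is already reportable under the protocol. The case report form is not among the documents, so whether inability to stand is a coded field must be checked before the derivation is written.
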